4.2.4 Administration Details for Obinutuzumab for Expansion Cohort

The recommended dosage of obinutuzumab is 1000 mg administered on Day 1, Day 8 and Day 15 of the first treatment cycle, followed by 1000 mg administered on Day 1 only for each subsequent 28-day treatment cycle.

Required premedication for management of infusion-related reactions is outlined in Section 7.4.2. Hypotension may occur during obinutuzumab IV infusions. Consider withholding antihypertensive treatments for 12 hours prior to and throughout each obinutuzumab infusion, and for the first hour after administration.

All patients in the dose-finding arm will receive TLS prophylaxis prior to cycle 1 day 1. Subjects in the expansion cohort who start obinutuzumab in cycle 4 will be considered for TLS prophylaxis on a case-by-case basis. Those with high tumor burden, high circulating absolute lymphocyte counts (>25 x10⁹/L), or renal impairment are considered at risk for TLS and should receive prophylaxis prior to cycle 4 day 1 if they are not already on appropriate TLS prophylaxis. Continue prophylaxis prior to each subsequent obinutuzumab infusion, as needed. During the initial days of obinutuzumab treatment, monitor the laboratory parameters of patients considered at risk for TLS (labs on Day 1, 2, 8, and 15). See Section 7.4.1 and Appendix G for details of TLS prophylaxis.

No dose reductions will be allowed for obinutuzumab on this protocol. For patients with toxicity potentially attributable to obinutuzumab including grade 3 or 4 neutropenia and/or febrile neutropenia, doses of obinutuzumab should be delayed up to two weeks until the toxicity improves to grade 1 or 2, or permanently discontinued if recovery does not occur within a two-week window. Patients who develop PML should be permanently discontinued from obinutuzumab therapy. Patients who develop a grade 4 infusion-related reaction or recurrent grade 3 infusion-related reactions should be discontinued permanently from obinutuzumab treatment on this trial.

4.2.5 Dose Modification Guidelines for Expansion Cohort

General principals/stopping rules: Dose Levels for the phase I portion of the study are as per Table 2. During the Expansion Cohort portion of the trial, dose delays/modifications are per the tables below and should be used as long as patients are deriving clinical benefit from the treatment regimen. Once the dose of an agent has been reduced, no dose re-escalation is permitted. If a scheduled dose is delayed for more than 6 weeks due to treatment-related toxicity, remove the patient from protocol therapy. No more than three dose reductions are permitted. A missed dose should not be made up, so that cycle lengths are always 28 days irrespective of the number of doses delivered in that cycle.

There will be no dose reductions for obinutuzumab. Dose reductions for CC-486 and venetoclax are per Table 4 below.

NOTE: Dose delays/dose reductions for the Dose Expansion portion of the study will be re-evaluated at the conclusion of the phase I portion of the study, and the following section is subject to revision.

Table 3A. Dose Modifications for Hematologic Toxicities. See Dose Levels for venetoclax and CC-486 in Table 4.

Observation	Action	Comments
Neutropenia ≥ gr 3	 Hold venetoclax, CC-486, and obinutuzumab (if applicable) Resume therapy at same dose level once neutropenia resolves to ≤ grade 2 If recurs, reduce by one dose level. If recurs again, reduce by one additional dose level. If recurs again, reduce by one additional dose level. 	Monitor CBC weekly. Consider use of growth factor support. If treatment is delayed by more than 6 weeks due to treatment-related toxicity, remove patient from study No more than 3 dose reductions are allowed
Thrombocytopenia ≥ gr 3	 Hold venetoclax, CC-486, and obinutuzumab (if applicable) Resume therapy at same dose level once thrombocytopenia resolves to ≤ grade 2 If recurs, reduce by one dose level. If recurs again, reduce by one additional dose level. If recurs again, reduce by one additional dose level. 	Monitor CBC weekly. No more than 3 dose reductions are allowed If treatment is delayed by more than 6 weeks due to treatment-related toxicity, remove patient from study
Anemia ≥ grade 3	 For first instance of grade 3 and 4 anemia, transfuse PRBC's as required If recurs, hold treatment and evaluate etiology (drug-related or not). If drug-related, 	Monitor CBC weekly. No more than 3 dose reductions are allowed If treatment is delayed by more than 6 weeks due to treatment-related toxicity, remove patient from study

decrease by one dose level. • If recurs again, reduce by one additional dose	
level.If recurs again, reduce by one additional dose level.	

Table 3B. Dose Modifications for non-Hematologic Toxicities. See Dose Levels for venetoclax and CC-486 in Table 4.

Observation	Action	Comments
AE resolves promptly with supportive care	Maintain dose level	
Febrile neutropenia or neutropenia with infection	 Withhold all agents until resolution of fever and infection (as applicable) 	
Grade 3 or higher non- hematologic AE that does not resolve to grade 2 or	 Hold venetoclax, CC- 486, and obinutuzumab (if applicable) 	Monitor CBC and CMP weekly.
below within one week despite maximum supportive care	• Resume therapy at same dose level once AE resolves to ≤ grade	No more than 3 dose reductions are allowed
	 If recurs, reduce by one dose level. If recurs again, reduce by one additional dose level. 	If treatment is delayed by more than 6 weeks due to treatment-related toxicity, remove patient from study
	If recurs again, reduce by one additional dose level	

Table 4. Venetoclax and CC-486 Dose Levels to be used if dose modifications are needed as per Tables 3A and 3B in the Expansion Cohort.

Agent	Starting Dose	Dose Reduction #1	Dose Reduction #2	Dose Reduction #3
Venetoclax	RP2D dose and schedule	RP2D dose on Days 1-10 only	50% reduction in dose, on Days 1-10 only	75% reduction in dose, on Days 1-10 only

and schedule same schedule same schedule with every other day dosing
--

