4.2.2 Administration Details for CC-486 for Expansion Cohort

All efforts should be made to administer CC-486 on all scheduled days. A dose missed earlier in a day can be administered later that day as long as it is taken at least 8 hours before the next scheduled dose. Any missed dose should not be taken beyond the last scheduled day of CC-486 administration

for the cycle, but should be returned by the subject for CC-486 accountability. If vomiting occurs after a dose of CC-486 is administered, that dose should not be made up later that day. The subject should continue with the dosing schedule on the next day and inform the treating investigator about the vomiting event at the next visit.

For the purposes of dose adjustment, unacceptable toxicity will be defined as any treatment related AE that is deemed by the treating investigator to be related to CC-486 and/or to the combination of CC-486 with venetoclax and/or obinutuzumab, and that poses a medical risk or substantial discomfort to the subject including, but not limited to, Grade 3 or 4 hematologic or non-hematologic toxicity. CC-486 dosing may be re-escalated (up to the planned dose level in the dose-finding cohort or the RP2D in the expansion cohort) at the discretion of the treating investigator. See Dose Modification Table 3 and Table 4 in Section 4.2.5.

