4.2.3 Administration Details for Venetoclax for Expansion Cohort

The dosing of venetoclax in this trial assumes the drug will be administered with a meal, and patients will be instructed to take venetoclax immediately prior to a meal. On days when venetoclax is taken with CC-486, venetoclax should be given first.

If vomiting occurs within 15 minutes after taking venetoclax and all expelled tablets are still intact, another dose may be given. Otherwise, no replacement dose is to be given. In cases where a dose of venetoclax is missed or forgotten, the patient should take the dose as soon as possible and ensure that the minimal interval between the current dose and the next dose is at least 16 hours in order to avoid excessive drug accumulation after the next dose.

All patients must receive prophylaxis for tumor lysis syndrome (TLS) with antihyperuricemics (e.g., allopurinol or rasburicase) and ensure adequate hydration prior to start of venetoclax therapy (see Section 7.4.1 and Appendix G for further details). If TLS is diagnosed by laboratory criteria only AND resolves within 48 hours, venetoclax may be resumed at the prior dose without adjustment. If TLS is diagnosed by laboratory criteria AND lasts greater than 48 hours before full resolution OR TLS is diagnosed by clinical criteria, the dose of venetoclax should be reduced following Table 4.

For the purposes of dose adjustment, unacceptable toxicity will be defined as any treatment related AE that is deemed by the treating investigator to be related to venetoclax and/or to the combination of venetoclax with CC-486 and/or obinutuzumab, and that poses a medical risk or substantial discomfort to the subject including, but not limited to, grade 3 or 4 hematologic or non-hematologic toxicity. Treatment should be delayed if there is any evidence of infection until the resolution of any infection-related symptoms. After an episode of unacceptable toxicity resolves or after the first episode of an infectious complication which resolves within 3 weeks, venetoclax may be resumed or re-escalated to the prior dose at the discretion of the treating investigator. After a second or greater episode of an infectious complication which resolves within three weeks, the venetoclax dose should be adjusted as shown in Table 3 and Table 4. Treatment with investigational agents should not be resumed after an infectious complication that remains symptomatic for greater than 3 weeks.

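### Expansion-cohort toxicity rules contradict each other on dose re-escalation, and on whether a patient delayed more than 6 weeks leaves treatment or leaves the study

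*Combined protocol and SAP*

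**What the plan says.** **Scope.** Section 4.2.5 sets the general hold, reduction and delay rules and ties them to one cohort: "During the Expansion Cohort portion of the trial, dose delays/modifications are per the tables below". Table 4 gives the reduction steps "to be used if dose modifications are needed as per Tables 3A and 3B in the Expansion Cohort". Its first venetoclax step is "RP2D dose on Days 1-10 only".

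**Re-escalation.** Section 4.2.5: "Once the dose of an agent has been reduced, no dose re-escalation is permitted". Section 4.2.2: "CC-486 dosing may be re-escalated (up to the planned dose level in the dose-finding cohort", and the sentence goes on to name the RP2D as the ceiling in the expansion cohort, with the decision left to the treating investigator. Section 4.2.3, for the period after a toxicity or a first infection has resolved: "venetoclax may be resumed or re-escalated to the prior dose at the discretion of the treating investigator".

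**Delay of more than 6 weeks.** The text of 4.2.5 says to "remove the patient from protocol therapy". Table 3A says "If treatment is delayed by more than 6 weeks due to treatment-related toxicity, remove patient from study", and Table 3B carries the same comment.

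**Patients who stop for toxicity.** Section 3.12 lists unacceptable adverse events among the reasons to stop study treatment while monitoring continues. Section 3.13 keeps patients withdrawn from treatment for an AE enrolled and in the intention-to-treat analysis. Section 5.9 moves them to the end-of-treatment visit and then to post-treatment follow-up. Section 6.3 defines the expansion analysis set as assigned patients who received at least one dose.

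**After a DLT.** Section 6.2.1 says what the next patients receive. It does not say how the patient who had the DLT is treated.

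**The concern.** A site that has reduced an expansion patient's dose finds one sentence forbidding a return to the earlier dose and two others permitting it. Sites can therefore treat the same event differently without departing from the protocol. Dose received then varies by site for a reason unrelated to the patient, in a single-arm cohort meant to estimate activity at the RP2D.

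The removal wording touches the endpoints directly. The primary endpoint needs the PET before cycle 7. The secondary endpoints need PFS and OS follow-up and the 30-month PET. A patient taken off the study at a 6-week delay has none of the assessments still to come, yet remains in the analysis set.

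**Working it through.** The plan's only figures nearby are the Simon design values in 6.1. Exact enumeration of the rule in 6.2.2 (stop at 5 or fewer of 15; reject at 13 or more of 32; 30% versus 50%) gives alpha 0.0997, power 0.8038 and early-stopping probability 0.7216 under the null. These match the plan, and the point does not affect them. The rest is a comparison of text plus one dosing calculation.

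1. **Are the re-escalation rules about the same patients?** Yes. Section 4.2.5 is worded for the expansion cohort. Section 4.2.2 is headed for that cohort, names its RP2D as the ceiling and refers to Tables 3 and 4. Section 4.2.3 has the same heading. No order of precedence is given.

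2. **Can they be reconciled?** For venetoclax, partly. Returning to the prior dose in 4.2.3 could mean restarting after a hold, and Table 3A does restart at the same dose after a first neutropenia or thrombocytopenia. For CC-486, no: re-escalating up to the RP2D presupposes a dose below it.

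3. **When does the conflict arise?** Under Tables 3A and 3B a reduction follows a recurrence, not a first event. The conflict therefore concerns patients already reduced.

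4. **How far apart are the two rules for venetoclax?** Inputs: doses from Table 2 and the first step from Table 4, assuming a continuous RP2D (4.2.1.2 has venetoclax taken every day of the cycle).
   - Dosing days: 10/28 = 0.357, a 64.3% cut. Ratio 28/10 = 2.8.
   - RP2D at DL 1: 400 × 10 = 4,000 mg per cycle if re-escalation is barred; 400 × 28 = 11,200 mg if the site returns to full schedule.
   - RP2D at DL 2: 600 × 10 = 6,000 against 600 × 28 = 16,800 mg.
   - RP2D at DL 3: 800 × 10 = 8,000 against 800 × 28 = 22,400 mg.

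5. **Does the bar reach too far?** As written it covers any reduction. Section 4.2.3 requires a venetoclax cut of at least 75% with azole prophylaxis, and 4.5 a cut of at least 50% with P-gp agents. Read literally, the bar would keep such a patient on the low dose after the interacting drug is stopped.

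6. **Removal.** For what is in substance one trigger, a treatment-related delay of more than 6 weeks, the text of 4.2.5 ends therapy and the tables end study participation. Sections 3.12, 3.13 and 5.9 agree with the text. Section 6.3 keeps the patient in the denominator. The tables are the exception and the only wording that stops assessment.

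**The case against.** **The table comment is shorthand.** Several operative sections keep these patients in follow-up, and a careful site would follow them. This stands in part: the loss occurs only if the table is followed literally. But Tables 3A and 3B are what a site consults when toxicity occurs, and nothing in them points to 3.13.

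**The section will be reviewed anyway.** Section 4.2.5 is marked as subject to revision after phase I, and 6.2.2 requires a review of the dose-modification plan before expansion starts. That is in time for the cohort where both contradictions apply. It offers an occasion to correct them but does not say which rule governs.

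**Stronger readings a reader might infer, which the documents do not support:**

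- *Each removed patient costs 1/32 = 3.1 points of the CR rate.* That is a ceiling. The patient stays in the denominator, and the rate changes only if a CR would have been recorded.
- *The discontinuation rate is biased by a knowable amount.* It is a primary endpoint of the dose-finding cohort (2.7), while the direct contradictions lie in expansion. The figure of under 15% in 1.2.2.2 is an expectation, not a decision boundary.
- *Dose-finding patients have no toxicity management.* Rules for infection, infusion reactions and TLS (7.4, Appendix G) and unacceptable adverse events (3.12) are not limited to one cohort. The narrower point is that no general hold or reduction rule clearly applies to them.
- *Table 3A should therefore cover both cohorts.* A hematologic DLT needs grade 4 toxicity lasting more than 7 days or with hemorrhage. Holding all drugs at grade 3 neutropenia or thrombocytopenia in cycle 1 would cut exposure inside the 28-day DLT window and could push the RP2D upward unless evaluability is defined.
- *Table 4 fails because its first step is no reduction from DL -2.* That depends on an optional level being reached and then carried into a section due for review. Section 4.2.1.2 presumes daily venetoclax.

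**Conclusion.** The point holds for two contradictions in the expansion cohort: whether a reduced dose may be raised again, and whether a treatment-related delay of more than 6 weeks ends therapy or ends study participation. The size of the first is a 2.8-fold difference in venetoclax per cycle after Dose Reduction #1, assuming a continuous RP2D and a patient already reduced, which under Tables 3A and 3B means after a recurrence. The second has no computable size. Its consequence, loss of later response and survival assessments in patients kept in the analysis set, depends on sites following the tables literally. No effect on the CR or discontinuation rate is claimed.

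A secondary gap is that 6.2.1 does not say how a patient is treated after a DLT, and 4.2.5 gives no hold or reduction rule clearly meant for dose-finding patients. This is missing detail rather than contradiction.

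**What to change.** 1. In Tables 3A and 3B, replace removal from the study with an instruction to discontinue study treatment and follow per Section 3.13.
2. Let one re-escalation rule govern. Delete the re-escalation sentence in 4.2.2 and the words *or re-escalated* in 4.2.3, so that the bar in 4.2.5 applies to toxicity reductions. State that it does not cover azole or P-gp interaction cuts. The deleted 4.2.2 sentence also mentions dose-finding patients, so say whether the bar covers them.
3. Optionally, state in 6.2.1 that after a non-fatal DLT treatment is held until grade 2 or lower and may resume one step lower if the lead PI agrees. Say that this takes precedence over the same-dose resumption in Table 3A and does not override mandatory permanent stops, such as obinutuzumab after a grade 4 infusion reaction.
4. Do not extend the Table 3A grade 3 holds to dose-finding patients in cycle 1 without a rule for DLT evaluability.

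The cost is protocol wording only. Items 1 and 2 can be settled at the review that 6.2.2 already requires before expansion. The sample size and the Simon boundaries are unchanged.

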4.3 PREPARATION AND ADMINISTRATION OF STUDY DRUG

Venetoclax and CC-486 tablets will be delivered to, stored, and dispensed from the University of Chicago Medicine Investigational Drug Service (IDS) Pharmacy. A 28-day supply of each drug will be provided to patients in bottles. Obinutuzumab vials will be delivered to, stored, and dispensed from the IDS and administered intravenously in the infusion center of University of Chicago Medicine or the participating study sites.

4.4 SUBJECT COMPLIANCE MONITORING

For the oral medications CC-486 and venetoclax, study personnel will review the dosing instructions with the subject prior to dispensing the study drug. The subject will be instructed to return any unused study drugs to the site at the next visit. Subject compliance will be noted on the appropriate CRFs and source records based on a tablet count. To monitor treatment compliance, reconciliation of tablet will be done at each scheduled study visit. Exposure to the therapy will also be assessed by a reliable history, diary, and expected pharmacologic effect during the follow-up visits.

4.5 CONCOMITANT MEDICATIONS AND THERAPIES

All treatments that the treating investigator considers necessary for a participant's welfare may be administered at the discretion of the treating investigator in keeping with the standards of medical care. All concomitant medication will be recorded on the case report form (CRF) including all prescription, over-the-counter (OTC), herbal supplements, and IV medications and fluids. If changes occur during the trial period, documentation of drug dosage, frequency, route, and date may also be included on the CRF. All concomitant medications received within 28 days before the first dose of trial treatment and 30 days after the last dose of trial treatment should be recorded. Concomitant medications administered after 30 days after the last dose of trial treatment should be recorded for SAEs and Adverse Events of Special Interest.

Participants are prohibited from receiving the following therapies during the screening and treatment phase of this trial:

- Anti-neoplastic biological therapy
- Immunotherapy not specified in this protocol
- Chemotherapy
- Steroid therapy for anti-neoplastic intent
- Investigational agents other than venetoclax, CC-486, or obinutuzumab
- Radiation therapy
- Live vaccines within 30 days prior to the first dose of study treatment and while participating in the study. See Section 3.4. Examples of live vaccines include, but are not limited to, the following: measles, mumps, rubella, varicella/zoster, yellow fever, rabies, BCG, and typhoid vaccine. Seasonal influenza vaccines for injection are generally killed virus vaccines and are

allowed; however, intranasal influenza vaccines (eg,FluMist®) are live attenuated vaccines and are not allowed.

- Strong and moderate CYP3A inhibitors (see Appendix H)
- CYP3A inducers (see Appendix H)
- Warfarin or warfarin derivatives
- P-gp inhibitors or narrow therapeutic index P-gp substrates

NOTE: There is an interaction between P-gp substrates/inhibitors and venetoclax. If these agents become required, reduce the venetoclax dose by at least 50%.

In addition, in order to avoid overestimation of the MTD, moderate or strong CYP3A inducers are prohibited during the DLT Evaluation Period.

Concomitant medications that fall into the categories below could potentially lead to adverse reactions and should be considered cautionary (except where noted). If a potential study patient is taking any of the medications in the categories described below, the treating investigator must assess and document the use of medications known or suspected to fall in the following medication categories:

- Moderate/weak CYP3A inducers such as efavirenz and oxcarbazepine
- CYP2C8 substrates such as thiazolidinediones (glitazones) and select statins (because of expected inhibition of the metabolism of CYP2C8 substrates) by venetoclax
- CYP2C9 substrates such as tolbutamide (because of expected inhibition of the metabolism of CYP2C9 substrates by venetoclax). It is recommended to exclude CYP2C9 substrates with a narrow therapeutic index such as phenytoin.

Patients who use oral contraceptives, hormone-replacement therapy, or other maintenance therapy should continue their use.

4.5.1 Monitoring and Treatment for Hepatitis B Reactivation

Patients who are both HBsAg negative and hepatitis B core antibody (anti-HBc) positive may be included in this study. These patients should have HBV DNA levels obtained monthly for at least 12 months after the last cycle of therapy by means of real-time PCR with the use of an assay that has a sensitivity of at least 10 IU/mL.

If the HBV DNA assay becomes positive and is above the World Health Organization's cutoff of 100 IU/mL, treatment with immunochemotherapy should be held and the patient should be treated (for at least 1 year after the last dose of obinutuzumab) with an appropriate nucleoside analogue and immediately referred to a gastroenterologist or hepatologist for management. Patients may resume immunochemotherapy once HBV DNA levels decrease to undetectable levels.

If the HBV DNA assay becomes positive and is ≤ 100 IU/mL, the patient should be retested within 2 weeks. If the assay is still positive, treatment with obinutuzumab must be held and the patient should be treated with an appropriate nucleoside analogue (for at least 1 year after the last dose of obinutuzumab) and immediately referred to a gastroenterologist or hepatologist for management. Patients may resume obinutuzumab once the HBV DNA levels decrease to undetectable levels.

If a patient's HBV DNA level exceeds 100 IU/mL while the patient is receiving antiviral medication, treatment with immunochemotherapy must be permanently discontinued.

